*** Subject Population ***

5. Subject Population

a) **Describe proposed subject population, stating age range, gender, race, ethnicity, language and literacy.**

We will recruit study participants in the East Bay area of Northern California, from the cities of Rodeo, Hercules, Tara Hills, Pinole, El Sobrante, San Pablo, Richmond, El Cerrito, Albany, Berkeley, Oakland, and Alameda. This area has a total population over 850,000 people and contains census tracts ranked in the top 10th percentile statewide for highest aggregate socio-demographic and environmental burdens, including several in the top 99th-100th percentile for asthma burden.

The study population will consist of children age 6-12 with and without asthma who live in homes with gas stoves and range hoods that vent to the outdoors. As of 2019, there are approximately 120,000 children ages 5-17 living in these cities. Using 2014 data 10-20% of those children have asthma. We plan to recruit up to 60 families, a very small percentage of the available population.

We anticipate that the study population will reflect the greater area population and therefore be roughly 50% male, 50% female, 32% non-Hispanic White, 19% non-Hispanic Black, 18% non-Hispanic Asian. Roughly 25% will be Hispanic or Latinx. (These estimates use 2019 Census bureau 5 year estimates).

b) **State the maximum number of subjects planned for the study. This number should account for all subjects to be recruited, including those who may drop out or be found ineligible. Explain how number of subjects needed to answer the research question was determined.**

There will be 120 subjects (60 children and 60 parent's guardians) recruited, as per the power analyses below. If the household has more than one eligible child, only one will be eligible for recruitment. One caregiver in each household will also be recruited/enrolled.

Power for Exposure Analyses. In THE AQUA study the adjusted mean difference in PM2.5 between homes that used the stove hood (ever) and those that never did was 5 mcg/m3 (standard deviation 8.24). [35] Using Cohen's equations for t-tests (assuming alpha= 0.05 and beta=0.2), if we expect to see at least a 7 mcg/m3 difference with an intentional cooking ventilation intervention, we would expect to be able to detect that difference with 23 households in each group. Belanger and colleagues[32] showed that the average NO2 level in suburban American homes was roughly 10 ppm, and homes that use gas stoves have NO2 levels 2-5 times those that do not.[19,57] Thus we estimate that a ventilation intervention in homes with gas cooking could decrease NO2 7 ppb. To detect a different of this size requires 28 families per group; ours will have 30.

Power for Clinical Analyses. An intentional use of kitchen ventilation may decrease the PM2.5 levels by 10 mcg/m3 or more, which could decrease FeNO 7 ppb based on work by Mar et al.[26] The minimum detectable change in FeNO for a group size of 30 is 3.3 ppb. As some of the patients may be on corticosteroids, we also calculated a minimum sample size of those off daily medications; that sample size is 24 children. Stanojevic et al[58] report that the coefficient of variation for FEV1 in late childhood and early adolescence is roughly 10%, suggesting a standard deviation of roughly 10. For 30 per group, the minimum detectable effect size will be 0.296, or a minimum detectable FEV1 difference of 2.9 percent of predicted.

Protocol Title: AIM to improve Indoor Air: Airflow Improvements during Meal-prep

Protocol Type: Biomedical Non-Exempt

Date Submitted: 05/30/2022

Important Note: This Print View may not reflect all comments and contingencies for approval. Please check the comments section of the online protocol. Questions that appear to not have been answered may not have been required for this submission. Please see the system application for more details.

We might recruit up to 65 child/guardian pairs to allow for dropouts.

c) If any proposed subjects are children/minors, prisoners, pregnant women, those with physical or cognitive impairments, or others who are considered vulnerable to coercion or undue influence, state rationale for their involvement.

Inclusion of Women and minorities

All children ages 6 to 12 and their families in our study area will be eligible for the study regardless of gender, race or ethnicity. We anticipate that the study population will reflect the diversity of the area as described in 5a.

Inclusion of Children

As this study aims to evaluate an intervention for the homes of children, it is necessary to include children in the study. The study will recruit children ages 6-12- those younger than age six will be excluded as they are unlikely to be able to cooperate with the breathing test techniques (spirometry and exhaled nitric oxide). Drs. [name] and [name] have both conducted prior work with children, and as a board-certified pediatrician, [name] has extensive experience working with children.

6. Recruitment

a) Explain how, where, when, and by whom prospective subjects will be identified/selected and approached for study participation. If researcher is subject's instructor, physician, or job supervisor, or if vulnerable subject groups will be recruited, explain what precautions will be taken to minimize potential coercion or undue influence to participate. See CPHS Guidelines on Recruitment for more information.

We will recruit from East bay clinics where children are seen, using contacts previously established by the investigators. The Contra Costa Health System (CCHS) Clinics and UCSF Benioff Children's Physicians-Hilltop Pediatrics Clinic expressed their support (beginning in 2018) to serve as recruitment sites. We will post recruitment fliers in the clinic (see Recruitment Tear off flyer in attachments), and have study information cards that physicians can give to children with asthma (see RecruitmentCards in attachments). Physicians will be clear that whether or not the patient participates in the research project will have no effect on their patient-doctor relationship and that as a research study there may be no direct benefit on the patient's asthma, as included in the script.

Due to the paucity of in-person visits happening at the Contra Costa County Health Clinics and Hilltop (due to COVID), recruitment at those sites was supplemented in the spring of 2021 with a postcard mailing to all patients aged 6-12 with a diagnosis of asthma (see PostcardCCHS and PostcardHilltop in attachments). The postcard design was developed in collaboration with each clinic so as to be something that their clinic is comfortable providing to their patients. We provided the printed postcards, stamps and printable address labels to the clinics and they will identify patients in their system and send the mailings. No patient information will be provided to any other members of the study team. Those at the clinics will access patient PHI solely for purposes of recruitment, which is necessary for the research, and no PHI will be removed, physically or electronically, from the clinics.

As of April 2021, Lifelong-Jenkins clinic, Kiwi pediatrics and UCSF Benioff Children's Hospital Oakland (BCHO) Outpatient clinics are also willing to assist with recruitment. We will post recruitment fliers in the clinics (see Recruitment Tear off flyer in attachments), and we have study information cards (see RecruitmentCards in attachments) that physicians and staff can give to children with asthma. Physicians

Protocol Title: AIM to improve Indoor Air: Airflow Improvements during Meal-prep

Protocol Type: Biomedical Non-Exempt

Date Submitted: 05/30/2022

Important Note: This Print View may not reflect all comments and contingencies for approval. Please check the comments section of the online protocol. Questions that appear to not have been answered may not have been required for this submission. Please see the system application for more details.

and staff will be clear that whether or not the patient participates in the research project will have no effect on their patient-doctor relationship and that as a research study there may be no direct benefit on the patient's asthma, as included in the script.

We are also going to post recruitment fliers and leave recruitment cards in community spaces where kids and families may spend time (e.g., local library), at other clinics where no staff are participating in any recruitment activities (not handing out cards or otherwise). We will also post a digital version of our recruitment card on the West Contra Costa School District Digital Bulletin Board and at the appropriate newsletter/e-bulletin board for other school districts in our study area. We will provide digital flyers to other community organizations that regularly distribute materials to families, for inclusion in their outreach (newsletters, digital bulletin boards). We have also developed a social media kit (Facebook post, Instagram post and twitter post) that can be used by local community organizations to share information about the study. Drafts of all these are attached and, in all cases, interested people are referred back to our email and phone number. No community organizations will be involved in recruitment or screening in any way.

We have a webpage for the study at <https://cerch.berkeley.edu/research-programs/aim-study-airflow-improvements-during-meal-prep>. The webpage uses the same language and graphics as our recruitment materials. We have also set up a Facebook page for the study (using the same graphics with the same pre- approved language as the website and recruitment cards), which we will use to post the Facebook post shared above, so that others can share it from our posting. We will not communicate with anyone about the study on Facebook, instead referring them to our phone or email. Study staff will not be provided with access to any private Facebook groups, but rather the appropriate administrator of any Facebook groups will make the posts using the approved recruitment language, on behalf of investigators.

b) Describe any recruitment materials (e.g., letters, flyers, advertisements [note type of media/where posted], scripts for verbal recruitment, etc.) and letter of permission/cooperation from institutions, agencies or organizations where off-site subject recruitment will take place (e.g., another UC campus, clinic, school district). Attach these documents in Attachments section. Please see eProtocol Attachments Check List for Non-Exempt Applications for more information.

Recruitment materials attached include:

1- a flyer with tear off contact information for posting in the lobby of the recruiting clinics
2- recruitment note cards to be handed out by clinicians to the parents of patients with asthma (this text will be the same on versions that have graphics on the reverse- the same graphics as the recruitment postcards)
3- scripts for recruitment (including for clinicians when giving out note cards and for recruitment phone or email contacts)
4- digital recruitment flyers including both letter size versions and social media optimized graphics, as well as accompanying social media text

c) Will anyone who will be recruiting or enrolling human subjects for this research receive compensation for each subject enrolled into this protocol? If yes, please identify the individual(s) and the amount of payment (per subject and total).

No.

Protocol Title: AIM to improve Indoor Air: Airflow Improvements during Meal-prep

Protocol Type: Biomedical Non-Exempt

Date Submitted: 05/30/2022

Important Note: This Print View may not reflect all comments and contingencies for approval. Please check the comments section of the online protocol. Questions that appear to not have been answered may not have been required for this submission. Please see the system application for more details.

7. Screening

a) Provide criteria for subject inclusion and exclusion. If any inclusion/exclusion criteria are based on gender, race, or ethnicity, explain rationale for restrictions.

We will recruit children ages 6-12. They will be eligible for this study if:

-they live in Rodeo/Hercules/Pinole/Tara Hills/El Sobrante/Richmond/San Pablo/El Cerrito/Albany/Berkeley/Oakland/Alameda
-they are between 6-12 years old
-they have both a gas stove and a range hood that exhausts to the outdoors.
-they live a majority of the time at one household

They will be excluded from the study for:

-living with a smoker who smokes indoors
-if they know they will not have stable housing for the next 3 months
-not fluent in English

b) If prospective subjects will be screened via tests, interviews, etc., prior to entry into the "main" study, explain how, where, when, and by whom screening will be done. NOTE: If screening data will be used for research purposes beyond determining eligibility, consent must be obtained for screening procedures as well as "main" study procedures. As appropriate, either: 1) create a separate "Screening Consent Form;" or 2) include screening information within the consent form for the main study.

At the time of initial recruiting contact, a brief screening interview will be conducted. Due to the COVID-19 pandemic, all recruitment and screening will occur remotely. Study subjects will call the study after being exposed to our recruitment materials. When a parent/guardian calls our phone number to express interest in the study, study staff will return the phone call and perform the screening interview over the phone, getting a verbal consent for screening first (using the unsigned screening consent form). Screening Data will be recorded so that included and excluded participants can be compared.

The study staff will ask if the child is age 6-12, if they have been diagnosed with asthma by a physician (though they are eligible whether or not they have asthma), if they have any other medical conditions, if they live with any smokers, if they have plans to move in the next few months, whether they are fluent in english, whether they have a gas stove in their home and whether they have a range hood that vents to the outdoors.

8. Compensation and Costs

a)

Describe plan for compensation of subjects. If no compensation will be provided, this should be stated. If subjects will be compensated for their participation, explain in detail about the amount and methods/ terms of payment.

Include any provisions for partial payment if subject withdraws before study is complete.

Protocol Title: AIM to improve Indoor Air: Airflow Improvements during Meal-prep

Protocol Type: Biomedical Non-Exempt

Date Submitted: 05/30/2022

Important Note:
This Print View may not reflect all comments and contingencies for approval. Please check the comments section of the online protocol.
Questions that appear to not have been answered may not have been required for this submission. Please see the system application for more details.

When subjects are required to provide Social Security Number in order to be paid, this data must be collected separately from consent documentation. If applicable, describe security measures that will be used to protect subject confidentiality.

If non-monetary compensation (e.g., course credit, services) will be offered, explain how

At the time of each in-person study visit, families will be given a \$20 Visa gift card, such that by the end of the three visits they will have received \$60 total (in visa gift cards). An additional \$40 in gift cards will be given to the families at the final visit if all study equipment has been returned, in working order. Furthermore, after assessment of airflow through the range hood, all hoods with inadequate flow will be replaced (where feasible). Thus, in addition to monetary compensation, families will get either a verification that their range hood is functioning adequately, or a new replacement hood.

b) Discuss reasoning behind amount/method/terms of compensation, including appropriateness of compensation for the study population and avoiding undue influence to participate.

\$100 is an appropriate amount to compensate the child and their guardian for their time. Given that there is the additional benefit of a replacement hood (or verification that theirs functions with adequate airflow), we feel this compensation balances the risk of coercion with the need to adequately compensate the participants.

c) Costs to Subjects. If applicable, describe any costs/charges which subjects or their insurance carriers will be expected to pay. (If there are no costs to subjects or their insurers, this should be stated.)

There will be no cost to the insurers. It is possible that there could be a slight increase in electricity use by the subjects due to the use of our measuring devices or increased use of their range hood, but this should be no more than a few dollars over the duration of the study. Other than this, there are no costs to the subjects. Subjects are not liable for lost, stolen or damaged equipment.

Protocol Title: AIM to improve Indoor Air: Airflow Improvements during Meal-prep

Protocol Type: Biomedical Non-Exempt

Date Submitted: 05/30/2022

Important Note: This Print View may not reflect all comments and contingencies for approval. Please check the comments section of the online protocol. Questions that appear to not have been answered may not have been required for this submission. Please see the system application for more details.

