#### Power Considerations

This is a pilot study, and with COVID-related delays and adjustments, we were not able to complete the study with enough households to be fully powered for either exposure analyses or respiratory health outcomes (especially as the study was modified to include all children, rather than only those with asthma). However, the initial power calculation is retained here, to document the intended recruitment and that we acknowledge that we are underpowered.

In THE AQUA study the adjusted mean difference in  $PM_{2.5}$  between homes that used the range hood (ever) and those that never did was  $5 \mu g/m^3$  (standard deviation 8.24). (19) Using Cohen's equations for t-tests (assuming  $\alpha = 0.05$  and  $\beta=0.2$ ), if we expect to see at least a  $7 \mu g/m^3$  difference with an intentional cooking ventilation intervention, we would expect to be able to detect that difference with 23 households. Belanger and colleagues(21) showed an average  $NO_2$  level in homes of kids with asthma in Massachusetts was roughly 10 ppb, and low-income homes that use gas stoves a lot ( $>1h/day$ ) have  $NO_2$  levels 2-5 times those that do not.(6) In a study out of Lawrence Berkeley Lab, in homes expected to have high  $NO_2$ ,  $NO_2$  levels were roughly 10 ppb higher in homes with gas cooking. Thus we estimate that a ventilation intervention in homes with gas cooking could optimistically decrease  $NO_2$  7 ppb. To detect a difference of this size requires 28 households.

An intentional use of kitchen ventilation may decrease the  $PM_{2.5}$  levels by  $10 \mu g/m^3$  or more, which could decrease FeNO in asthmatic children by 7 ppb based on work by Mar et al, showing a decrease in FeNO based on prior day  $PM_{2.5}$  averages.(23) The minimum detectable change in FeNO for a group size of 30 is 3.3 ppb. Stanojevic et al (24) report that the coefficient of variation for FEV1 in children with asthma is around this age is roughly 10%, suggesting a standard deviation of roughly 10. For 30 children, the minimum detectable effect size will be 0.296, or a minimum detectable FEV1 difference of 2.9 percent of predicted.

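### The detectable FEV1 effect of 0.296 SD (2.9 points) cannot be reproduced from the stated inputs, and the SAP drops the per-group label from three of the retained sizes

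*Protocol*

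**What the plan says.** Protocol section 5b bases the planned 60 children on its power analyses. The exposure paragraph gives a method: "Using Cohen's equations for t-tests (assuming alpha= 0.05 and beta=0.2"). From a PM2.5 difference of 7 mcg/m3 and an SD of 8.24 it concludes: "we would expect to be able to detect that difference with 23 households in each group". For NO2: "To detect a different of this size requires 28 families per group; ours will have 30". No SD is given for NO2.

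The clinical paragraph takes a coefficient of variation of about 10% for FEV1, "suggesting a standard deviation of roughly 10", and ends: "For 30 per group, the minimum detectable effect size will be 0.296, or a minimum detectable FEV1 difference of 2.9 percent of predicted". It names no test, power, sidedness or within-child correlation.

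Protocol section 9a describes one before-after group in which every family receives the intervention.

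The SAP (Power Considerations) says that the initial calculation is kept to document the intended recruitment, and that the study is underpowered. Three of the four sizes lose their group label:

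- PM2.5: "we would expect to be able to detect that difference with 23 households".
- NO2: "To detect a difference of this size requires 28 households".
- FEV1: "For 30 children, the minimum detectable effect size will be 0.296, or a minimum detectable FEV1 difference of 2.9 percent of predicted".

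The FeNO sentence still refers to a group of 30. The SAP's Study Design section lists 2 + 5 + 7 = 14 households that completed the study.

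**The concern.** An effect of 0.296 SD is small for 30 per group or for 30 children in total. The same number cannot follow from both sizes under one method with the same inputs, and the stated method gives it for neither.

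This is the only statement in the documents of what the study can detect on FEV1, and the Protocol cites these analyses as the basis for its sample size. A reader who later meets a non-significant FEV1 result may take 2.9 points as the change that the study was built to see, and cannot check that.

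The wording change in the SAP adds a second difficulty. A calculation kept as a record of intended recruitment now reads as if about 30 households had been intended, while the Protocol planned 60.

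**Working it through.** **Inputs from the documents.** Alpha 0.05 and power 0.80 (Protocol 5b, exposure paragraph); PM2.5 difference 7 and SD 8.24; FEV1 SD about 10; sizes 30 (FEV1), 60 (planned children) and 14 (completed households).

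**Assumptions.** Tests are two-sided, with one-sided tests also tried. The FEV1 SD of 10 is the SD of levels between children. The within-child correlation r is not given, so it is shown as a range.

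**Step 1. Reproduce the plan's own figure.** For PM2.5, d = 7/8.24 = 0.85. A two-sample t-test (noncentral t) needs n = 22.8, so 23 per group. This matches the Protocol.

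**Step 2. Apply the same method to FEV1.**

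| Design | Detectable d, two-sided | One-sided |
|---|---|---|
| 30 per group | 0.736 SD of levels (7.4 points) | 0.650 |
| 30 children, paired | 0.529 SD of change | 0.465 |
| 60 children, paired | 0.368 SD of change | 0.325 |

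None of these is 0.296. Read backwards, 80% power at 0.296 needs 181 per group (180.1), or 92 pairs (91.5) if 0.296 is in SDs of change. At the stated sizes, 0.296 has about 20% power with 30 per group and about 35% with 30 pairs.

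A smaller point: 0.296 × 10 = 2.96, so the printed 2.9 is either truncated or rests on an SD near 2.9/0.296 = 9.8.

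**Step 3. What would produce 0.296?** If it is in units of the between-child SD, the SD of change is 10 × √(2(1 − r)), so r = 1 − (0.296/d)²/2.

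- 30 pairs: 1 − (0.296/0.529)²/2 = 0.84.
- 60 pairs: 1 − (0.296/0.368)²/2 = 0.68.
- 14 pairs (d = 0.810): 1 − (0.296/0.810)²/2 = 0.93.

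**Step 4. Detectable change in points**, d × 10 × √(2(1 − r)):

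| Children, before-after | d (SD of change) | r = 0.5 | r = 0.7 | r = 0.9 |
|---|---|---|---|---|
| 60 (planned) | 0.37 | 3.7 | 2.8 | 1.6 |
| 30 | 0.53 | 5.3 | 4.1 | 2.4 |
| 14 (most available) | 0.81 | 8.1 | 6.3 | 3.6 |
| 12 | 0.89 | 8.9 | 6.9 | 4.0 |
| 10 | 1.00 | 10.0 | 7.7 | 4.5 |

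The rows for 12 and 10 are illustrative. The SAP includes only children with successful tests before and after the intervention, and does not say how many there are.

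**Step 5. The SAP's own test.** A simulation of the Wilcoxon signed rank test (20,000 runs, normally distributed changes) gave 78% power at n = 60 with d = 0.368, and 79% at n = 14 with d = 0.81. The t-test figures are slightly optimistic.

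**Step 6. Are 23 and 28 too small as totals?** If 8.24 is the SD of levels, a paired t-test for 7 mcg/m3 needs 23.7 homes at r = 0, 22.9 at r = 0.04 and 12.9 at r = 0.5. If 8.24 is the SD of change, it needs 12.9, so 13. As a before-after total, 23 is therefore adequate at any correlation above about 0.04. The 28 for NO2 cannot be checked, because no SD is given.

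**The case against.** The strongest reply is that the t-test is stated only for PM2.5 and the FEV1 sentence does not claim it. Part of the Protocol is also not available for review. For 60 children measured before and after, 2.9 points lies inside the range in Step 4 and is reached at r of about 0.69. This stands. A reader might infer that 0.296 is an arithmetic error or impossible. The documents do not support that; they show only that an input is missing.

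A reader might also infer that the SAP understates the homes needed by turning per-group sizes into totals. Step 6 does not support that for 23, nothing can be shown for 28, and the FeNO sentence keeps its group wording. It is also tempting to say that the group wording comes from the abandoned two-group stepped-wedge design. That is likely, since the SAP describes such a design, but neither document says so.

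Finally, the SAP calls the study an underpowered pilot, and no analysis or decision rule uses 0.296. This limits the consequence. It does not make 2.9 points checkable: the concession is about too few households, whereas the figure cannot be reproduced even at the intended size.

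**Conclusion.** The point holds as a minor documentation matter. From an SD of about 10, alpha 0.05 and 80% power, the stated 0.296 SD follows neither for the Protocol's 30 per group (0.74 SD, about 2.5 times larger) nor for the SAP's 30 children (0.53 SD of change, about 1.8 times larger if the SD of change is also 10). It requires an input that neither document states. With 14 children or fewer, 2.9 points would need a within-child correlation of about 0.93 or higher.

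The non-reproduction depends on carrying the PM2.5 method over to FEV1. The point values depend also on reading 10 as a between-child SD and on the assumed correlations. The SAP's relabelling of three sizes is inaccurate as a record, but no more than that.

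**What to change.** In SAP Power Considerations, and in Protocol 5b if it is amended:

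1. Either state the test, power and within-child correlation that gave 0.296, or replace it with the paired figure: 0.53 SD of change for 30 children and 0.37 for the planned 60, with points over a range of assumed correlations as in Step 4.
2. In the SAP, add the figure for the children actually available: at best 0.81 SD of change at 14 (8.1, 6.3 and 3.6 points at r = 0.5, 0.7 and 0.9). Note that the Wilcoxon test has slightly less power than the t-test used here.
3. Add a note that 23, 28 and the FEV1 30 were per-group sizes in the Protocol. Name the two-group design as their origin only if the sponsor confirms it.
4. Do not insert new PM2.5 or NO2 sizes. The documents do not settle whether 8.24 is an SD of levels or of a difference, and they give no SD for NO2.

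The cost is a few sentences. No participants, data or analyses change. The FEV1 figure in the SAP will look less favourable over the range shown; in the Protocol the direction depends on the correlation.
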